10.6. Safety Outcome Analysis

- Incidence of Mild Gastrointestinal Discomfort, SAEs, Withdrawals: Frequencies and percentages will be presented for both groups. Comparisons will be made using Fisher's Exact test for categorical data, particularly where low event counts are expected. Risk Differences with 95% CI will be reported.
- Transient Diarrhea in Diabetic Participants: This will be reported descriptively as the number and percentage of affected participants. No formal statistical test will be applied due to expected rarity.

10.7. Baseline Characteristics Analysis

- Descriptive statistics (mean \pm SD for continuous variables; frequencies and percentages for categorical variables) will summarize baseline characteristics for both treatment groups.
- T-tests (for continuous variables) and Chi-square tests (for categorical variables) will be used to confirm that the randomization process resulted in balanced groups.

11.1. Definition of Adverse Events (AEs) and Serious Adverse Events (SAEs)

- Adverse Event (AE): Any untoward medical occurrence in a participant administered a pharmaceutical product and which does not necessarily have a causal relationship with this treatment.
- Serious Adverse Event (SAE): Any AE occurring at any dose that results in death, is life-threatening, requires inpatient hospitalization or prolongation of existing hospitalization, results in persistent or significant disability/incapacity, is a congenital anomaly/birth defect, or is otherwise considered by the investigator to be an important medical event.

11.2. Reporting Procedures for AEs and SAEs

- AEs: All AEs will be recorded in the participant's daily diary and subsequently transferred to the CRF by the investigator. Information collected will include onset date, resolution date, severity (mild, moderate, severe), relationship to study product (not related, unlikely related, possibly related, probably related, related), and outcome.
- SAEs: All SAEs must be reported immediately (within 24 hours of investigator awareness) to the Sponsor and the central IRB. Detailed SAE reports will include all relevant clinical information, causality assessment, and outcome. Follow-up reports will be submitted as new information becomes available.

11.3. Data Safety Monitoring Board (DSMB)

- An independent Data Safety Monitoring Board (DSMB) will be established to provide ongoing safety oversight. The DSMB will comprise independent experts in gastroenterology, clinical pharmacology, and biostatistics, who are not involved in the conduct of this study.
- The DSMB will receive blinded aggregated safety data on a weekly basis during the intervention phase.
- The DSMB will have the authority to recommend modifications to the protocol, temporary suspension, or termination of the study if significant safety concerns arise.

12. Ethical Considerations

12.1. Institutional Review Board (IRB) Approval This protocol, the Informed Consent Form (ICF), participant recruitment materials, and any subsequent amendments will be reviewed and approved by the Nimsai Academia Ethics Committee prior to study initiation at Nimsai Academia. The study will not commence until full Ethics Committee approval has been obtained.

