6.1. Randomization Procedure

- Eligible participants will be randomized in a 1:1 ratio to either the Nimsai Herbal group or the placebo group.
- A computer-generated randomization sequence will be prepared by an independent third party (a contract research organization or a statistician not involved in study conduct) prior to the start of the study.
- The randomization sequence will be stratified by hemorrhoid severity (Grade 2 vs. Grade 3) to ensure an even distribution of severity across treatment arms.
- Study medication kits will be pre-packaged and labeled with unique randomization numbers. Once a participant is enrolled, the next sequential randomization number will be assigned.

6.2. Blinding Method This study will employ a quadruple-blind design, meaning the participant, the care provider, the investigator, and the outcomes assessor will all be blinded to the treatment assignment.

- Product Appearance: Nimsai Herbal and placebo capsules are identical in appearance, color, taste, and packaging.
- Packaging and Labeling: Study medication will be packaged in identical, opaque containers with only the randomization number and essential safety information displayed.
- Allocation Concealment: The randomization list will be securely maintained by the independent third party and will not be accessible to study personnel or participants.

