6.3. Unblinding Procedures

- Emergency Unblinding: In the event of a medical emergency where knowledge of the assigned treatment is absolutely necessary for the participant's care (severe adverse reaction suspected to be related to the study product), emergency unblinding may occur. This will be performed by authorized personnel (unblinded pharmacist or designated study staff) following a pre-defined procedure. The reason for unblinding and the time/date will be thoroughly documented.
- Planned Unblinding: The full unblinding of the study results will only occur after the completion of all data collection, database lock, and final statistical analyses have been performed. An unblinded statistician, not involved in interim analyses or study conduct, will have access to the unblinded data for final analysis.

7. Outcome Measures

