7.3.2. Incidence of Serious Adverse Events (SAEs)

- Name: Incidence of Serious Adverse Events (SAEs)
- Definition: Percentage of participants experiencing SAEs as defined by ICH GCP guidelines (death, life-threatening event, inpatient hospitalization, persistent or significant disability/incapacity, congenital anomaly/birth defect, or any other important medical event).
- Time Frame: Baseline to Day 10.
- Unit of Measure: Incidence (%).
- Assessment Method: Continuous monitoring, immediate reporting to IRB/DSMB, and documentation on CRFs.

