- **Interim Analysis:** No interim analyses are planned for this study, given its short duration (10 days) and the low expected risk of serious adverse events (SAEs).

3. Outcome Measures and Statistical Analysis

This section details the statistical methods for each predefined outcome measure.

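### The weekly safety report to the DSMB is blinded and aggregated, with no stated route to data by arm, so it may not show whether harm is concentrated on active treatment

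*Protocol*

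**What the plan says.** Protocol 11.3 sets up an independent board with expertise in gastroenterology, clinical pharmacology and biostatistics, whose members take no part in running the study. On what it sees: "The DSMB will receive blinded aggregated safety data on a weekly basis during the intervention phase". On what it may do: it has "authority to recommend modifications to the protocol, temporary suspension, or termination of the study if significant safety concerns arise".

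Three other places bear on whether the board could learn the arm:

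- Protocol 6.2, allocation concealment: "The randomization list will be securely maintained by the independent third party and will not be accessible to study personnel or participants". No release to the DSMB is described.
- Protocol 6.3: emergency unblinding is for the care of one participant. For the end of the trial, "An unblinded statistician, not involved in interim analyses or study conduct, will have access to the unblinded data for final analysis".
- SAP section 2: "No interim analyses are planned for this study".

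On individual SAEs the protocol says two different things. Section 7.3.2 gives the method as "Continuous monitoring, immediate reporting to IRB/DSMB, and documentation on CRFs". Section 11.2 says: "All SAEs must be reported immediately (within 24 hours of investigator awareness) to the Sponsor and the central IRB". It does not name the DSMB.

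**The concern.** In a 1:1 placebo-controlled trial, the most direct way to ask whether the product causes harm is to compare the arms. The final safety analysis does this: protocol 10.6 and SAP 3.3 prescribe Fisher's exact test and risk differences between arms for gastrointestinal discomfort, SAEs and withdrawals due to adverse events. The board that reviews safety while participants are being dosed is promised no such comparison.

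If the weekly tables are totals over both arms, an excess on active treatment and an even split look the same. The board would then have to make a recommendation on continuing the trial without the most informative fact about the events. The inconsistency over SAE reporting adds to this, because it leaves unclear whether the board's other source of information exists in practice.

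**Working it through.** The documents give no figure for the DSMB's task: no expected event count, background rate or alert threshold. The event totals below are therefore assumptions.

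**Inputs.** 150 per arm, 300 in total (protocol 3.3). Two-sided Fisher's exact test, as in protocol 10.6. Study period 10 October to 14 November 2021 (protocol 3.2): 35 days / 7 = about five weekly reports. All 300 participants are counted; earlier reports would cover fewer.

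**Step 1. What a pooled total conveys.** If a events fall on active and b on placebo, a pooled table shows (a + b)/300. Every split with the same sum gives the same table.

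**Step 2. What the split would have shown.** With equal arms, a complete split of k events has p = 2 × C(150, k) / C(300, k).

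- 7 v 0: 2 × 0.00727 = 0.0145. For 4 v 3, p = 1.0. Both appear as 7/300 = 2.33%.
- 12 v 2: the upper-tail terms for 12, 13 and 14 are 0.004779 + 0.000681 + 0.000044 = 0.005504; doubled, p = 0.0110. For 7 v 7, p = 1.0. Both appear as 14/300 = 4.67%.

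**Step 3. How this depends on the assumed total.**

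| Split | Fisher p |
|---|---|
| 3 v 0 | 0.25 |
| 4 v 0 | 0.12 |
| 5 v 0 | 0.06 |
| 6 v 0 | 0.030 |
| 6 v 1 | 0.12 |
| 7 v 0 | 0.015 |
| 8 v 0 | 0.007 |

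With five or fewer events, no split reaches 0.05. At such counts, by-arm tables help through clinical judgement and not through a test.

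**Step 4. What a pooled total can still do.** Suppose the background rate were known, and an alarm were raised when the pooled total of 300 exceeded it at a one-sided 2.5% level. With an assumed 2% on placebo and 8% on active, the threshold is 12 events and the chance of an alarm is 0.825; the by-arm Fisher test has power 0.582. If the background were wrongly taken as 4%, the threshold becomes 20 events and the chance falls to 0.117. So pooled monitoring can work well, but only with a reliable reference rate, and the documents state none.

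**Step 5. Is there another route to the arm?** Read together, 6.2, 6.3, 11.3 and the SAP's interim-analysis statement provide no closed report, no DSMB access to the code and no unblinded statistician before the final analysis. Sections 7.3.2 and 11.2 do not mention the arm in connection with SAE reports. Under either section, a single SAE report would not show an imbalance.

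**The case against.** The strongest reply is that pooling is an interpretation. The text speaks of blinded, aggregated data; it does not say that the arms are combined. Aggregated could mean summary tables as opposed to listings, and blinded could mean columns masked as A and B. In that case 7 v 0 and 4 v 3 would look different. This stands as far as it goes: masked tables are not excluded. But the board would then see an imbalance without knowing its direction, no route to the code is described, and the text should say which is meant.

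Second, a reader might infer that the board sees nothing but totals, that it can stop the trial itself, or that the safeguard cannot work. The documents support none of these. Section 7.3.2 also sends SAEs to the DSMB. Section 11.3 gives power to recommend, not to stop. A high total, or one SAE with the clinical detail and causality assessment required by 11.2, could prompt a recommendation without any comparison of arms; step 4 shows that totals can be a sensitive alarm when the background is known. Nor does 11.2 exclude the DSMB; it omits it, so this is a mismatch to reconcile and not proof of a closed route.

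Third, treatment lasts 10 days and the SAP expects a low risk of SAEs. At low counts even by-arm data would not be conclusive. That limits the practical impact. It does not explain why an independent board should be kept from the comparison.

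Fourth, by-arm review might seem to threaten blinding or to spend alpha. It need do neither if the report holds safety data only, involves no test of the primary outcome, and stays between the third party and the board.

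**Conclusion.** The concern holds in a limited form. On the natural reading of 11.3 the weekly report cannot show whether events are concentrated on active treatment, and nothing elsewhere in the protocol or SAP supplies that information. This limits the board's basis for a recommendation; it does not remove it. On the masked A/B reading the gap narrows to not knowing the direction.

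The size depends on assumed counts. At 150 per arm, splits as different as 7 v 0 and 4 v 3, or 12 v 2 and 7 v 7, give identical pooled tables, while at five events or fewer no split would reach 0.05. That a pooled total carries no information on the split does not depend on these counts.

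Separately, and on any reading, 7.3.2 and 11.2 disagree on whether the DSMB is among the recipients of immediate SAE reports. Both matters should be corrected. Given the short treatment and the low expected SAE risk, this is an improvement that the sponsor should make; it is not a fatal flaw.

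**What to change.** 1. **Protocol 11.3.** Replace the blinded, aggregated data with a closed weekly report of AEs, SAEs and withdrawals by arm, coded A/B, with the code available to the DSMB. The independent third party that already holds the randomization list should prepare it. Sponsor, site and outcome assessors stay blinded.
2. **Same section.** State that the report contains no efficacy data and no formal test, so that it agrees with the SAP's statement on interim analyses, and that imbalances over about five weekly looks are judged clinically, since some will arise by chance.
3. **Protocol 6.3.** Add the DSMB's access to the code as an exception to the rule that full unblinding waits until after the final analyses.
4. **Protocol 11.2 and 7.3.2.** Reconcile the two on SAE reporting to the DSMB.

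If the sponsor did mean masked tables, 11.3 should say so and state how the board can obtain the code.

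The cost is wording in these sections and in the board's procedures, plus a small amount of table production behind a firewall. No extra participants, visits or tests are needed.

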12.2. Informed Consent Process

- Written informed consent will be obtained from every participant prior to the performance of any study-specific procedures.
- The investigator or a designated qualified member of the study team will thoroughly explain the study objectives, procedures, potential risks and benefits, alternatives, and the participant's right to withdraw at any time without penalty.
- Participants will be given sufficient time to read the ICF, ask questions, and consider their participation before signing. A copy of the signed ICF will be provided to the participant.

12.3. Participant Rights and Confidentiality

- The rights and well-being of all participants will be protected throughout the study in accordance with the Declaration of Helsinki and ICH GCP guidelines.
- Participant confidentiality will be maintained at all times. All data collected will be de-identified through the use of unique participant identification numbers. No individual participant's name or other direct identifiers will be used in any reports or publications. Access to confidential records (medical history, consent forms) will be restricted to authorized personnel only.

12.4. Data Protection Regulations All data collection, processing, and storage will comply with applicable local and international data protection regulations (GDPR equivalents, HIPAA, local privacy laws) to ensure the privacy and security of participant information.

13. Investigator Responsibilities

13.1. General Responsibilities The Principal Investigator at Nimsai Academia is responsible for the overall conduct of the study in accordance with this protocol, ICH GCP, and all applicable regulatory requirements.

13.2. Training and Qualification All investigators and study staff will be qualified by education, training, and experience to perform their assigned tasks. They will receive specific training on this protocol, study procedures, and data collection tools.

13.3. Protocol Adherence Investigators are responsible for ensuring strict adherence to the approved protocol. Any deviations from the protocol must be documented, justified, and reported to the Sponsor and IRB/EC as required.

14. Data Handling and Record Retention

14.1. Documentation Standards All study data will be recorded accurately, completely, and legibly on CRFs, participant diaries, and source documents. Any corrections will be made according to GCP guidelines, ensuring the original entry remains legible and the correction is dated and initialed.

14.2. Retention Period All study-related documents, including CRFs, ICFs, source documents, and regulatory approvals, will be retained for a minimum of 15 years after the completion of the study or as required by local regulations, whichever is longer. Documents will be stored in a secure, accessible location.

15. Publication Policy

17.1. Appendix A: Case Report Forms (CRFs)

17.2. Appendix B: Participant Daily Diary

17.3. Appendix C: Informed Consent Form (ICF)

Statistical Analysis Plan (SAP): (Protocol NA-2024-01)

Official Title: Double-Blind, Placebo-Controlled, Parallel-Group Randomized Controlled Trial to Evaluate the Efficacy and Safety of Nimsai Herbal in Patients with Grade 2-3 Hemorrhoids

NCT Number: NCT07034820

Protocol Number: NA-2024-001

Document Date: October 10, 2021

Version: 2

Sponsor: Nimsai Academia Bursa, Türkiye

Principal Investigator: [name] Nimsai Academia

Center [contact]

Email: [contact]

Prepared by: Nimsai Academia Bursa, Türkiye

Submission Format: PDF/A

Confidentiality Statement: This document contains confidential information and is intended solely for authorized personnel, investigators, and regulatory authorities. Unauthorized reproduction or distribution is prohibited. No participant names or identifiable information are included.

1. Introduction

This Statistical Analysis Plan (SAP) outlines the detailed methodology for the statistical analysis of data collected during Protocol NA-2024-01, double-blind, placebo-controlled, parallel-group Randomized Controlled Trial evaluating the efficacy and safety of Nimsai Herbal in patients with Grade 2-3 hemorrhoids. This SAP is developed in conjunction with the study protocol (Protocol ID: NA-2024-01) and adheres to the principles of ICH Good Clinical Practice (GCP).

2. General Statistical Approach

- **Analysis Populations:** Analyses will be conducted on an intention-to-treat (ITT) basis, including all randomized participants regardless of treatment adherence or protocol deviations. A per-protocol (PP) sensitivity analysis will also be performed to assess the robustness of the primary findings, including only participants who completed the study as per protocol and had no major deviations.
- **Missing Data Handling:** Missing data for primary and secondary outcomes will be handled using appropriate methods, primarily multiple imputation if data are considered missing at random (MAR). Sensitivity analyses using Last Observation Carried Forward (LOCF) or complete case analysis will also be performed where appropriate.
- **Software:** Statistical analyses will be performed using validated statistical software, specifically SAS (Statistical Analysis System) or R.
- **Significance Level:** All statistical tests will be two-tailed, and a significance level of $\alpha=0.05$ will be used to determine statistical significance.
- **Interim Analysis:** No interim analyses are planned for this study, given its short duration (10 days) and the low expected risk of serious adverse events (SAEs).

3. Outcome Measures and Statistical Analysis

This section details the statistical methods for each predefined outcome measure.

3.1. Primary Outcome: Hemorrhoid Regression Rate

- **Name:** Hemorrhoid Regression Rate
- **Definition:** Percentage of participants achieving a clinical response, defined as a $\geq 75\%$ reduction in composite hemorrhoid severity score from baseline.
- **Time Frame:** Day 10 (end of treatment and follow-up period)
- **Statistical Test:** Chi-square test
- **Method:** Comparison of categorical data (proportion of participants achieving $\geq 75\%$ reduction) between the Nimsai Herbal group and the placebo group.
- **Effect Size:** Risk Difference with a 95% Confidence Interval (CI).
- **Power Calculation:** Based on an assumed 50% regression rate in the Nimsai Herbal group and 20% in the placebo group, a sample size of 150 participants per arm (total 300) provides $>90\%$ power to detect a statistically significant difference at an $\alpha=0.05$ (two-tailed) significance level.

3.2. Secondary Outcomes

3.2.1. Visual Analog Scale (VAS) Symptom Score Change

- Name: Visual Analog Scale (VAS) Symptom Score Change
- Definition: Mean change in self-reported hemorrhoid symptom severity from baseline to Day 10, measured on a 0–10 Visual Analog Scale.
- Time Frame: Baseline to Day 10
- Statistical Test: Mann-Whitney U test
- Method: Non-parametric comparison of continuous data (change in VAS scores) between the Nimsai Herbal and placebo groups. This test is chosen due to the expected non-normal distribution of patient-reported symptom scores.
- Effect Size: Mean Difference with a 95% CI.
- Adjustment: Baseline VAS scores may be included as a covariate in sensitivity analyses to account for any residual imbalance or improve precision.

3.2.2. Symptom Resolution Rate

- Name: Symptom Resolution Rate
- Definition: Percentage of participants reporting complete resolution of baseline hemorrhoid symptoms (pain, bleeding, itching, swelling), defined as a composite severity score of 0.
- Time Frame: Day 10
- Statistical Test: Chi-square test
- Method: Comparison of categorical data (proportion of participants with complete symptom resolution) between the Nimsai Herbal and placebo groups.
- Effect Size: Risk Ratio with a 95% CI.
- Adjustment: Logistic regression may be used to adjust for baseline hemorrhoid severity or other relevant covariates in supplementary analyses.

3.3. Safety Outcomes

3.3.1. Incidence of Mild Gastrointestinal Discomfort

- Name: Incidence of Mild Gastrointestinal Discomfort
- Definition: Percentage of participants reporting mild gastrointestinal adverse events (e.g., nausea, bloating, dyspepsia) during the study period.
- Time Frame: Baseline to Day 10
- Statistical Test: Fisher's Exact test
- Method: Comparison of categorical incidence data between the Nimsai Herbal and placebo groups. Fisher's Exact test is chosen due to the expected low event frequencies.
- Effect Size: Risk Difference with a 95% CI.

3.3.2. Incidence of Serious Adverse Events (SAEs) and Withdrawals Due to Adverse Events

- Name: Incidence of Serious Adverse Events (SAEs) / Incidence of Withdrawals Due to Adverse Events
- Definition: Percentage of participants experiencing SAEs or discontinuing treatment/withdrawing due to AEs.
- Time Frame: Baseline to Day 10
- Statistical Test: Fisher's Exact test (if events occur)
- Method: Comparison of incidence data between groups. If no events are observed in either group, descriptive reporting will be provided (0% incidence).
- Effect Size: Risk Difference with a 95% CI.

